11.2.2 Randomization and Blinding

11.2.3 Interim Analysis and Unblinding

There are no planned interim analyses. Other than individual subjects being unblinded for safety issues, the database will remain blinded until after the database is locked.

11.2.4 Data and Safety Monitoring Board

An independent Data and Safety Monitoring Board (DSMB) will be appointed to review and assess study conduct and safety for the duration of the clinical study.

11.3 Analysis Sets

The ITT and per protocol (PP) populations form the bases for the evaluation of efficacy. The safety (S) population forms the basis for the evaluation of safety

11.3.1 Intent-to-Treat (ITT) Population

The ITT population includes all randomized subjects with at least one efficacy measurement after receiving the 6.0 g dose (whether FT218 or placebo). A valid diary measurement is defined to include at least 3 days of entries per week. Diary measurements with fewer days will be treated as missing, and if there are no other measurements, will not qualify the subject for the ITT population. Subjects will be assigned to treatment arms in the analysis as randomized.

11.3.2 Per Protocol (PP) Population

The PP population includes all subjects in the ITT population reduced by those who failed to follow the protocol with respect to protocol deviations. These are, inclusion or exclusion criteria not satisfied ([Section 8.3.2](#) and [Section 8.3.3](#)); deviations related to study drug administration, deviations to the schedule of visits and procedures, or deviations related to non-permitted concomitant medications ([Section 8.4.8.1](#)). Subjects will be assigned to treatment arms as randomized.

11.3.2.1 Safety (S) Population

The S population includes all subjects that receive at least one dose of study drug. Subjects will be assigned to treatment arms based on the treatment actually administered (FT218 if active drug was administered at any time, placebo otherwise).

11.4 Description of Statistical Analysis

The formal statistical analysis and specific dose/placebo contrasts will be based on a mixed-effects repeated measures model. Descriptive statistics characterizing the study population and the observed outcomes will be produced.

11.4.1 General Considerations

All statistical tests will be performed using a 2-tailed 5% overall significance level, unless otherwise specified. Descriptive statistics will be provided by treatment arm and as a summary across both treatment arms.

11.4.2 Use of Analysis Sets

For the primary statistical analysis of efficacy endpoints, the ITT will be used; a supportive analysis will be carried out on the PP population unless it is essentially the same as the ITT population, if the difference in sample sizes is less than 10%. All safety endpoints analysis will be conducted on the S population.

11.4.3 Analysis of Subgroups

The primary efficacy analyses of EDS will be performed on the ITT population. The primary efficacy analyses for cataplexy will be performed on the NT1 subgroup of the ITT population.

11.5 Subject Disposition

The number of subjects within each treatment arm of each analysis population will be summarized. The number of subjects entering each period of the study will be tabulated along with the number of subjects who withdraw. The timing of withdrawal and reasons for withdrawal ([Section 8.3.4](#)) will be summarized by treatment arm for each period of the study and summarized over all periods in the randomized stage.

11.6 Demographic and Other Baseline Characteristics

Subject demographics will be presented by treatment arm and for the total study. Baseline will be defined as the last measurement before randomization. Initial data at screening will also be reported for all screened subjects.

Cases for which the entry criteria or other protocol requirements were violated will be identified and their baseline characteristics will be summarized.

11.7 Medical History

Medical history data will consist of significant conditions or diseases recorded during the screening process. Data will be tabulated using the Medical Dictionary for Regulatory Activities (MedDRA) primary system organ class (SOC) and preferred term for subjects in the S population.

11.8 Study Drug Exposure and Compliance

Study drug exposure and duration in the study will be derived based on first and last dose taken. Compliance will be computed as percentage of study drug taken.

11.9 Efficacy Analysis

11.9.1 Description of Primary Endpoints

The co-primary endpoints for evaluating EDS in both NT1 and NT2 subjects are the mean sleep latency on the MWT and the CGI. The MWT is the mean latency across 5 naps, averaged over the test day and the CGI is the clinician's global impression of improvement in daytime sleepiness from screening.

The primary endpoint for evaluating cataplexy is the NCA, which will be evaluated only in the NT1 subpopulation. The NCA is the mean number of cataplexy events recorded on the Sleep and Symptom Daily Diary during the period. Because of concern about the variability of this measure, a minimum number of diary entries of 3 per week will be required for the average to be considered an observation. If the number of days with entries is less than 3 per week, the mean NCA will be considered missing.

All ITT or PP subjects will be included in the evaluation of narcolepsy and all ITT or PP subjects with both conditions will be used in the evaluation of cataplexy.

11.9.1.1 Primary Analysis

A mixed-effects means model with repeated measures will be used to analyze change from baseline for each of the MWT and cataplexy endpoints. Each model will include treatment, time (at which the measurement was taken), treatment-by-time interaction, site and baseline score as fixed effects, and subjects as random effects. [REDACTED]

For CGI, a GLIMMIX model for binomial data with logit link will be used instead of a MMRM to analyze the categorized CGI response, i.e., proportion of patients who were very much or much improved. The observed values for the categorized response (very much or much improved versus other category) will be used as responses in the model. Each model will include treatment, time (at which the measurement was taken), treatment-by-time interaction and site as fixed effects and subjects as random effects. In fitting the model, time will range over the entire period of observations. The odds ratio, 95% confidence intervals for the odds ratio and p-value will be provided.

11.9.1.2 Sequential Testing Approach for Comparing FT219 and Placebo

The primary hypothesis tests of the efficacy of individual doses will be performed as contrasts within the mixed models. The hypothesis testing will proceed in the following order: first, to test

hypotheses for EDS, both MWT and CGI will be examined for statistical significance for the 9.0 g dose using the data collected during Period 3c(i), and 3c(ii). If both tests are significant, NCA for the same dose will be tested. If the first test fails (either MWT or CGI not significant), the data for the 9.0 g dose was not able to reject the null hypothesis of equality to placebo for either symptom. If the first test is significant (both MWT and CGI significant) but the second test (NCA) fails, the dose has been demonstrated to exceed placebo for EDS treatment but not for cataplexy. If both tests are statistically significant, the dose has been shown to be effective for EDS and cataplexy.

If the 9.0 g dose demonstrates efficacy for both EDS and cataplexy, the same sequence of testing will be followed for the 7.5 g dose using the data collected during Period 3b(i) and 3b(ii). If the 7.5 g dose demonstrates efficacy for both EDS and cataplexy, the same sequence of testing will be followed for the 6 g dose using the data collected during Period 3a.

Each dose will be tested at the 2-sided alpha level of 0.05. Efficacy tests for MWT and for CGI within a dose need not be adjusted, since both are required for demonstrating efficacy for EDS at that dose. Efficacy tests for NCA within a dose for demonstrating efficacy for cataplexy also need not be adjusted because the test is reached via a step down procedure. At each step, rejection terminates all subsequent hypothesis tests, which will be deemed to be non-significant. A strictly exploratory analysis examining secondary/exploratory endpoints is also proposed to provide evidence of consistency. The type I error rate for these endpoints will all be tested at the α level of 0.05.

Note: the testing of the efficacy of the 6.0 g dose is intended to address the question of identifying the minimally effective dose. If the 9.0 g dose and then the 7.5 g dose is effective on the primary outcome variables, hypothesis tests on the efficacy of the 6.0 g dose will be carried out.

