Each dose will be tested in a hierarchical order starting at the 9.0 g dose level at the 2-sided α level of 0.05. Efficacy tests for MWT and for CGI within a dose need not be adjusted, since both are required for demonstrating efficacy for EDS at that dose. Efficacy tests for NCA within a dose for demonstrating efficacy for cataplexy also need not be adjusted because the test is reached via a step down procedure. Within each step, rejection terminates all subsequent hypothesis tests, which will be deemed to be nonsignificant. A strictly exploratory analysis examining secondary/exploratory endpoints is also proposed to provide evidence of consistency. The type I error rate for these endpoints will all be tested at the α level of 0.05.

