2.4 SAMPLE SIZE DETERMINATION

Estimation of sample size to achieve a desired power depends on the number and nature of the hypothesis testing paradigm and assumptions about the magnitude of the underlying effects. In this trial, hypothesis testing will proceed in the following order. First MWT and CGI will be examined for statistical significance in the full sample including both NT1 and NT2 patients for the 9 g dose. If significant, NCA for the same dose will be tested in NT1 patients. If the first test fails, the data for this dose is not able to reject the null hypothesis of equality to placebo. If the first test is significant, but the second fails, the dose has been demonstrated to be superior to placebo for EDS treatment, but not for cataplexy. If both tests are statistically significant, the dose has been shown to be effective for both EDS and cataplexy treatment. The same sequence of testing will be followed for the 7.5 g dose. If both tests are statistically significant, the dose has been shown to be effective for both EDS and cataplexy treatment and the same sequence of testing will then be followed for the 6 g dose. Each dose will be tested at the two-sided alpha level of 0.05.

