4.6.2 SEQUENTIAL TESTING APPROACH FOR COMPARING SOCR AND PLACEBO

The primary hypothesis tests of the efficacy of individual doses will be performed as contrasts within the mixed models. The hypothesis testing will proceed in the following order, which is represented pictorially in Figure 1. First to test hypotheses for EDS, both MWT and CGI will be examined, in parallel for statistically significant differences from placebo for the 9 g dose. The order of hypothesis testing and the tests to be performed are displayed in Figure 1. For the 9 g dose, if both tests are significant, NCA for the same dose will be tested. If the first test fails (either MWT or CGI not significant), the data for the 9 g dose was not able to reject the null hypothesis of equality to placebo for either symptom. If the first test is significant (both MWT and CGI significant,) but the second test (NCA) fails, the 9 g dose has been demonstrated to exceed placebo for EDS treatment but not for cataplexy. If both tests are statistically significant, the 9 g dose has been shown to be effective for EDS and for cataplexy. Although all data are included in the full model, the tests for the 9 g dose are contrasts over the Periods 3c(i) and 3c(ii).

[figure not shown]
If the 9 g dose demonstrates efficacy for both EDS and cataplexy, the same sequence of testing will be followed for the 7.5 g dose using contrasts over the Periods 3b(i) and 3b(ii). If the 7.5 g dose demonstrates efficacy for both EDS and cataplexy, the same sequence of testing will be followed for the 6 g dose using contrasts over Period 3a.

Each dose will be tested at the two-sided alpha level of .05. Efficacy tests for MWT and for CGI within a dose need not be adjusted, since both are required for demonstrating efficacy for EDS at that dose. Efficacy tests for NCA within a dose for demonstrating efficacy for cataplexy also need not be adjusted because the test is reached via a step down procedure. Within each arm, rejection terminates all subsequent hypothesis tests, which will be deemed to be non-significant. A strictly exploratory analysis examining secondary/exploratory endpoints is also proposed to provide evidence of consistency. The Type I error rate for these endpoints will all be tested at the alpha level of .05.

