N.B. The testing of the efficacy of the 6 g dose is intended to address the question of identifying the minimally effective dose. If the 9 g dose and then the 7.5 g dose is effective on the primary outcome variables, hypothesis tests on the efficacy of the 6 g dose will be carried out.

Figure 1

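### The stopping sentence ends testing on rejection, against the plan's own gates, and SAP 2.4 goes on to 7.5 g with no condition on 9 g

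*Protocol*

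**What the plan says.** Protocol 11.9.1.2 and SAP 4.6.2 give the confirmatory order. At 9 g, MWT and CGI must both be significant for EDS; only then is NCA tested. The step to the next dose is gated on success: "If the 9.0 g dose demonstrates efficacy for both EDS and cataplexy, the same sequence of testing will be followed" at 7.5 g. The same condition applies from 7.5 g to 6 g. Each test is two-sided at 0.05, and Protocol 11.4.1 and SAP 4.1 set a 5% overall level.

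The same sections then state a stopping rule, which appears three times:

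- Protocol 11.9.1.2: "At each step, rejection terminates all subsequent hypothesis tests, which will be deemed to be non-significant".
- Protocol Synopsis: "Within each step, rejection terminates all subsequent hypothesis tests, which will be deemed to be nonsignificant".
- SAP 4.6.2: "Within each arm, rejection terminates all subsequent hypothesis tests, which will be deemed to be non-significant".

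Protocol 11.9.1.2 also shows what it means by the verb. If either MWT or CGI misses significance, the 9 g data "was not able to reject the null hypothesis of equality to placebo for either symptom".

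SAP 2.4 restates the order as background to the sample size. After 9 g it says only "The same sequence of testing will be followed for the 7.5 g dose". It then requires both 7.5 g tests to be significant, after which "the same sequence of testing will then be followed for the 6 g dose". The closing note of SAP 4.6.2 sets a stricter condition for testing 6 g: "If the 9 g dose and then the 7.5 g dose is effective on the primary outcome variables".

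**The concern.** There are two separate defects in the text that decides which claims the trial may make.

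1. **The stopping sentence is the wrong way round.** Rejection of the null is success, so the sentence ends testing on success. The gates in the same section continue on success. An analyst cannot follow both. The SAP version adds a further difficulty: in a two-arm trial whose single active arm passes through every dose, a rule applied within each arm does not identify a testing step.
2. **SAP 2.4 lacks the 9 g gate.** It states the condition for moving from 7.5 g to 6 g but none for moving from 9 g to 7.5 g. The two SAP sections part company when EDS succeeds at 9 g and NCA fails there: SAP 4.6.2 stops and SAP 2.4 goes on. Going on gives a second chance of a false claim at an unadjusted 5%.

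The first defect puts legitimate claims at risk. The second puts the familywise error at risk. This is a pivotal trial, so its decision rule should allow one reading before the data are unblinded.

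**Working it through.** **Inputs from the documents.** Two-sided 0.05 per test and 5% overall (Protocol 11.4.1 and 11.9.1.2; SAP 4.1 and 4.6.2). Sequence: 9 g EDS, 9 g NCA, 7.5 g EDS, 7.5 g NCA, 6 g EDS, 6 g NCA, which is 3 doses × 2 symptoms = 6 claims. EDS needs both MWT and CGI.

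**Assumptions.** The visible text gives neither the correlation between dose contrasts nor the power for EDS. Correlations from 0 to 0.9 and EDS power of 1, 0.9 and 0.8 are used.

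**Step 1: the plan's own figure.** Under the gates, a false claim requires rejecting the first true null that is reached, so the familywise error is at most 0.05. This reproduces the stated 5%. Simulation with 2,000,000 draws per correlation gave 0.0497 to 0.0502.

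**Step 2: the stopping sentence combined with the gates.**

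| 9 g EDS result | Gate says | Sentence says | Both applied |
|---|---|---|---|
| MWT and CGI both significant | test 9 g NCA | stop | stop |
| MWT or CGI not significant | stop | no stop | stop |

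Nothing after 9 g EDS can be reached: 1 of 6 claims. Only one 5% step is tested, so the error stays at or below 5%.

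**Step 3: SAP 2.4 as written.** The 9 g chain is EDS then NCA. The 7.5 g chain starts whatever happened at 9 g; 6 g follows only if both 7.5 g tests succeed. Take EDS effective at every dose with power 1, and NCA null at every dose. The 6 g NCA test is reached only after a 7.5 g NCA rejection, which is already a false claim, so

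FWER = P(9 g NCA or 7.5 g NCA rejected) = 0.05 + 0.05 − P(both rejected).

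Independent doses: 1 − 0.95² = 0.0975. For correlated doses, from the bivariate normal with critical value 1.96:

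| Correlation | FWER, exact | FWER, simulated |
|---|---|---|
| 0 | 0.0975 | 0.0975 |
| 0.3 | 0.0951 | 0.0953 |
| 0.5 | 0.0907 | 0.0904 |
| 0.7 | 0.0835 | 0.0834 |
| 0.9 | 0.0704 | 0.0707 |

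**Step 4: EDS power below 1.** With EDS power p at each dose, and EDS success independent of NCA and across doses, FWER = 0.10p − p² × P(both NCA rejected). P(both) is 0.05² = 0.0025 if independent and 0.10 − 0.0704 = 0.0296 at correlation 0.9.

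- p = 0.9: 0.090 − 0.81 × 0.0025 = 0.0880; 0.090 − 0.81 × 0.0296 = 0.0660.
- p = 0.8: 0.080 − 0.64 × 0.0025 = 0.0784; 0.080 − 0.64 × 0.0296 = 0.061.
- Gates, same case: 0.05p = 0.045 and 0.040.

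**Step 5: upper bound.** SAP 2.4 amounts to two gated chains, {9 g EDS, 9 g NCA} and {7.5 g EDS, 7.5 g NCA, 6 g EDS, 6 g NCA}. Each has error of at most 0.05, so the total cannot exceed 0.05 + 0.05 = 0.10 in any scenario.

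**The case against.** The strongest reply is that no competent analyst would be misled. The gates are written out in full. Declaring the later tests non-significant makes sense only after a failure, and the closing notes on the 6 g dose agree. Rejection may have been meant as rejection of the dose. This shows the intent convincingly. It also means the 1-of-6 figure describes a contradiction in the text rather than a likely outcome. It does not make the sentence right: the section uses reject in its standard sense, and the rule appears three times in confirmatory text.

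On the second point, SAP 2.4 is background to the sample size, whereas SAP 4.6.2 is the operative section. The study summary in SAP section 2 does make 7.5 g conditional on a significant 9 g result, and Protocol 11.2.1 calls the order hierarchical. SAP 2.4 could itself be read as continuing from success at 9 g. All of this weighs in favour of a conflict within the SAP rather than a gate missing from the whole plan. But the study summary does not say whether significance at 9 g includes NCA, which is exactly the case in dispute, and SAP 2.4 states one gate while leaving out the other. SAP Figure 1 may settle the order, but it was not shown in the copy reviewed.

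On size, all dose contrasts compare the same two randomized arms, so positive correlation is to be expected and 9.75% is the upper end for this scenario. If EDS success were fully shared across doses, 80% power with correlation 0.9 would give 0.8 × 0.0704 = 5.6%, not 6.1%. That is still above 5%.

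**Conclusion.** Both points hold. The stopping sentence is wrong as written. Its cost, if applied with the gates, is lost claims (1 of 6 reachable), with no inflation of error. SAP 2.4 omits the 9 g condition. If it governed, with EDS effective and NCA null at every dose, the familywise error would be 7.0% to 9.75% with EDS power near 1 and 6.1% to 7.8% at 80% power, for correlations from 0.9 down to 0 and EDS success independent across doses. The 80% range falls to 5.6% at correlation 0.9 if EDS success is shared across doses. The ceiling is 10%. These rates rest on assumed correlation and power; confidence in the two wording points is high. The procedure in Protocol 11.9.1.2 and SAP 4.6.2 is sound and controls the error at 5% once the sentence is corrected. This should be fixed, as a correction of text and not a change of method.

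**What to change.** Replace the stopping sentence in the Protocol Synopsis, Protocol 11.9.1.2 and SAP 4.6.2 with one common wording:

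> If any step fails to reach two-sided p<0.05 (for EDS, if either MWT or CGI fails), all subsequent hypotheses in the sequence 9 g EDS, 9 g NCA, 7.5 g EDS, 7.5 g NCA, 6 g EDS, 6 g NCA are not tested and are deemed non-significant.

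In SAP 2.4, add that 7.5 g is tested only if 9 g succeeds on MWT, CGI and NCA. In Protocol 11.2.1 and the SAP section 2 study summary, refer to the rule in Protocol 11.9.1.2 and SAP 4.6.2. Check that SAP Figure 1 agrees.

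The cost is one sentence in three places, one clause and two cross-references, before unblinding. Design, data and sample size are unaffected.

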6.5 Study Rationale

Sodium oxybate has shown significant efficacy for EDS and cataplexy in the treatment of NT1 and NT2. Flamel Technologies is proposing a new sodium oxybate drug product, FT218, which utilizes the company's proprietary Micropump technology. The proposed innovation is clinically relevant as the current marketed product, Xyrem, has to be taken twice during the night, 2.5 to 4 hours apart, which is a limitation.

The FT218 Phase 1 study (study PKFT218-1301) confirmed the expected PK properties of the FT218 formulation i.e. a release of the drug over at least 6 hours, a lower C_{max} and a residual plasma level at 8 hours after intake not significantly different than the reference. Overall, under the hypothesis of a PK exposure-clinical effect relationship, this study confirmed that FT218 will be as safe as the reference marketed product. The forced up-titration design of this study is expected to be particularly informative, allowing observations of efficacy and safety at 6.0, 7.5, and 9g doses. Three therapeutic doses will be tested under forced up-titration (6.0, 7.5, and 9.0 g) since no concentration/response relationship is known. The study allows for forced dose increments at fixed times from 4.5 g/night followed by 1.5 g/night increments until the final 9.0 g dose is reached. Subjects will remain on the 4.5 g dose for 1 week, the 6.0 g dose for 2 weeks, the 7.5 g dose for 5 weeks and the 9.0 g dose for 5 weeks. Evaluations for efficacy and safety for 6.0, 7.5, and 9.0 g will be done over a 12-week period (total of 13 weeks on study drug) relative to the placebo group.

The up-titration is based on the dosage schedule recognized as safe with Xyrem. A full efficacy assessment will occur for the 6.0 g/night dose after 3 weeks on study drug (including a titration from 4.5 g/night for the first week followed by 2 weeks at 6.0 g/night). The 7.5 g full efficacy

assessment will occur after 8 weeks on study drug (including 1 week at 4.5 g and 2 weeks at 6.0 g). A final titration occurs to maximum dose (i.e. 9.0 g). A full efficacy assessment will be done following 5 weeks on the final dose (that is following a total of 13 weeks on medication) relative to the placebo group. During both the 7.5 g and the 9.0 g 5-week treatment a partial efficacy assessment [REDACTED] will be carried out after 2 weeks on the respective doses.

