4.1.2 DEFINITION OF STUDY VISITS

Study visits are identified by the week of the visit.

At Week -1 (Baseline) a full baseline evaluation will take place. Thereafter with full efficacy assessments occurring at week 3 for the 6 g dose, week 8 for the 7.5 g dose and week 13 for the 9 g dose. Visits with partial efficacy assessments (MWT and PSG are excluded) occur following the first two weeks on the 7.5 g dose (week 6 day 1) and following the first two weeks on the 9 g (week 11 day 1).

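### A non-significant 6 g result would not show that 7.5 g is the minimally effective dose, because 6 g is assessed after 2 weeks at dose and the higher doses over 5

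*Protocol*

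**What the plan says.** The note closing Protocol 11.9.1.2 gives the reason for the last step of the hierarchy: "the testing of the efficacy of the 6.0 g dose is intended to address the question of identifying the minimally effective dose". The N.B. in SAP 4.6.2 also calls the test "intended to address the question of identifying the minimally effective dose". The test is reached only after 9 g and then 7.5 g have succeeded, and "Each dose will be tested at the 2-sided alpha level of 0.05".

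The schedule is in Protocol 6.5: "Subjects will remain on the 4.5 g dose for 1 week, the 6.0 g dose for 2 weeks", followed by "the 7.5 g dose for 5 weeks and the 9.0 g dose for 5 weeks". On the full assessments, which include MWT, the same section says: "A full efficacy assessment will occur for the 6.0 g/night dose after 3 weeks on study drug". Those for 7.5 g and 9 g come after 8 and 13 weeks on drug. SAP 4.1.2 adds partial assessments, without MWT or PSG, which "occur following the first two weeks on the 7.5 g dose (week 6 day 1) and following the first two weeks on the 9 g".

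Each dose is compared with placebo over the same calendar weeks. SAP 4.1.3 gives the windows as weeks 2 and 3 for 6 g, weeks 4 to 8 for 7.5 g and weeks 9 to 13 for 9 g. The 4.5 g starting week has no efficacy contrast.

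**The concern.** In a single ascending sequence, dose, time at dose and total exposure rise together. Concurrent placebo removes time trends common to both arms. It does not remove the difference in how long the active arm has been on each dose.

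Suppose 9 g and 7.5 g succeed and 6 g does not. Given the stated purpose, a reader would naturally take 7.5 g as the minimum. The same result could arise if 6 g were as effective as 7.5 g but had not had time to show it. The visible text does not warn against that reading. The direction of the error matters because Protocol 6.6 lists several dose-related adverse events that are most pronounced at 9.0 g and in some cases related to 7.5 g.

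**Working it through.** **1. The plan's own timings.** From Protocol 6.5: 1 week at 4.5 g, 2 at 6 g, 5 at 7.5 g, 5 at 9 g. Cumulative weeks on drug are 1 + 2 = 3, 3 + 5 = 8 and 8 + 5 = 13. These reproduce the stated weeks of the full assessments.

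| Dose | Weeks at dose when MWT is read | Weeks on drug | Weeks in the contrast (SAP 4.1.3) |
|---|---|---|---|
| 6 g | 2 | 3 | 2–3 |
| 7.5 g | 5 | 8 | 4–8 |
| 9 g | 5 | 13 | 9–13 |

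**2. What each outcome of the 6 g test supports.**
- *Significant:* 6 g beats concurrent placebo. It is the lowest studied dose shown to do so, and the short time at dose does not weaken that. Lower doses are not examined.
- *Not significant, after 7.5 g succeeded:* too low a dose, too short a time at dose and lower power are all compatible with the result.

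**3. How large the distortion could be.** The visible documents give no onset curve, so this part is assumption. Let 6 g and 7.5 g have the same full effect, and let the share present after *w* weeks be 1 − exp(−*w*/*t*), with *t* = 2 weeks. The ratio is the 6 g effect seen divided by the 7.5 g effect seen.

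*MWT* (single reading):
- Build-up restarts at each dose (2 v 5 weeks): 0.632/0.918 = 0.69.
- Weeks at 6 g or above count (2 v 7): 0.632/0.970 = 0.65.
- Weeks on any dose count (3 v 8): 0.777/0.982 = 0.79.

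*CGI* (effect taken on the model's log-odds scale; 7.5 g visits at 2 and 5 weeks weighted equally; restart): 0.632/[(0.632 + 0.918)/2] = 0.632/0.775 = 0.82.

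*NCA* (mean over the whole dose window; restart). The mean share over *w* weeks is 1 − (*t*/*w*)(1 − exp(−*w*/*t*)).
- 6 g: 1 − (2/2)(0.632) = 0.368.
- 7.5 g: 1 − (2/5)(0.918) = 0.633.
- Ratio: 0.368/0.633 = 0.58.

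Carry-over also moves the last two.
- Weeks at 6 g or above: CGI 0.632/[(0.865 + 0.970)/2] = 0.69. NCA 0.368/[1 − (2/5)(exp(−1) − exp(−3.5))] = 0.368/0.865 = 0.43.
- Weeks on any dose: CGI 0.777/[(0.918 + 0.982)/2] = 0.82. NCA [1 − (exp(−0.5) − exp(−1.5))]/[1 − (2/5)(exp(−1.5) − exp(−4))] = 0.617/0.918 = 0.67.

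The time constant matters as much. Restarting at each dose, the MWT ratio is 0.865/0.993 = 0.87 at *t* = 1 and 0.393/0.713 = 0.55 at *t* = 4.

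**4. What this does to the chance of a significant 6 g test.** The visible text gives no sample size or power, so take 90% power at the full 5-week effect as an illustration. If a fraction *f* of that effect is present, power is Φ(*f*(1.960 + 1.282) − 1.960).

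| *f* | One endpoint | All three endpoints, if independent |
|---|---|---|
| 1.0 | 90% | 73% |
| 0.8 | 74% | 40% |
| 0.6 | 49% | 12% |

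The last column is the cube of the one before. It applies because efficacy for both symptoms needs MWT, CGI and NCA.

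**5. The 6 g window.** Protocol 11.9.1.2 and SAP 4.6.2 place the 6 g contrast over Period 3a. SAP Table 1 defines Period 3a as weeks 1 to 3, including the 4.5 g week. SAP 4.1.3 and 4.1.5 use weeks 2 and 3. NCA is a mean over the period, so the Period 3a reading would mix 4.5 g days into the 6 g result.

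**The case against.** Three stronger readings are tempting, and the documents do not support them.

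- *Neither outcome identifies the minimum.* The documents do not define the term. The objectives compare only 6.0, 7.5 and 9.0 g with placebo. If it means the lowest studied dose superior to placebo, a 6 g success does identify it. Only the non-significant branch is in trouble.
- *The plan declares 7.5 g the minimum if 6 g fails.* No section says so. The note states an intention and sets no decision rule. Protocol 11.2.1 and SAP 2.4 describe a failed first test as an inability to reject the null hypothesis, which is not a finding of ineffectiveness. The wrong reading is one a user of the results might make.
- *One ratio of about 0.69 describes the shortfall.* That figure fits MWT only, with build-up restarting at each dose. CGI and NCA also use data from the first 2 weeks at the higher doses, and their ratios differ.

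The sponsor can also point to SAP 1.1, which says that increments beyond 6 g begin only once enough time has passed to evaluate efficacy. That is a direct answer, but it is asserted without onset data. Finally, subsections after Protocol 11.9.1.2 and SAP 4.6.2 are blacked out, so a qualification there cannot be excluded. If there is one, the note should point to it.

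**Conclusion.** The concern holds for one branch of the test. A non-significant 6 g result following success at 7.5 g would not establish 7.5 g as the minimum, because dose, time at dose and total exposure are confounded. A significant result stands as evidence for 6 g as the lowest studied dose superior to placebo.

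The ratios above rest on equal full effects at the two doses, exponential build-up and an invented time constant. They show that the distortion could matter, not that it does. With fast onset it would be small for the single MWT reading.

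Only interpretation is affected. The hierarchy's type I error, the 9 g test and trial conduct are untouched. Severity: minor.

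**What to change.** 1. In the note in Protocol 11.9.1.2 and the N.B. in SAP 4.6.2, state that the 6.0 g test assesses whether the lowest tested dose is superior to placebo after 2 weeks at that dose. Add that a non-significant result will not be read as showing that 6.0 g is ineffective or that 7.5 g is the minimum.

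2. Pre-specify one descriptive table, with no alpha, from the existing models, which already contain treatment-by-time terms. It shows FT218 against placebo at 2 weeks on each dose, with 95% confidence intervals:
   - CGI at Visits 4, 5 and 7, as odds ratios;
   - NCA over weeks 2–3, 4–5 and 9–10, as mean differences.

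   Use it as supportive context for any statement comparing doses, not as the sole basis. It has no MWT, and total exposure at those visits still differs (3, 5 and 10 weeks).

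3. Reconcile the 6 g analysis window between Period 3a (Protocol 11.9.1.2, SAP 4.6.2, SAP Table 1) and weeks 2–3 (SAP 4.1.3 and 4.1.5).

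The cost is wording in two documents, one extra table from data already collected, and a weaker dose-finding statement. No visit, dose or alpha changes.
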